3.3 Procedure

The study was conducted by two expert pediatric dentists. One of them gave all explanation, spoke with the children and carried out the anesthesia procedure and did the treatment procedure [name] and the other [name] was observing and assessing the children's pain perception.

In this study's cross-over design, children received both types of injections before filling/pulpotomy treatment on their maxillary primary molars in two separate appointments with a minimum interval of at least 1 week between procedures, on a side of the dental arch with the use of a needle free injection and on the other side with the traditional syringe. Type and sequence of administration to each individual were randomly assigned (using a coin). All dental equipment were introduced using 'tell-show-do technique. A total of 56 procedures were performed and divided into 2 groups according to the anesthesia technique. None of the children have undergone any previous dental local anesthetic experience, in order to be not influenced by a positive or negative memory.

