3.3.1 Injection with the needle-free (NF) system

The device used for needle free system was **Comfort-in™** (Mika Medical Global Co, Busan, Korea) anesthesia device (Figure 1). The **Comfort-in™ system**, has a micro-hole injection needle (0.15 mm) that injects the anesthetic solution under the mucosa. The pressure can be controlled according to the dose of the drug to be used, thereby reduced the pain that may occur with the needle in the injection. Before the injection procedure, the children were demonstrated the popping sound produced by device to prevent reflex reactions, and they informed that they would feel as if their gum were punched. The NF injection device was prepared according to the manufacturer's instructions, placed in full contact with the buccal mucosa and a pre-withdrawn dose of 0.1 ml was applied to the buccal region for topical purposes by the pushing the top of the device. After 10-15 seconds, the same procedure was repeated with withdrawn dose of 0.3 ml. After 5 min the treatment commenced, and the children were instructed to raise their hand if they experienced pain during the procedure. Each time the child indicated pain, in accordance with the same protocol an additional 0.3 ml of anesthetic solution was administered, until the sufficient anesthetic effect was obtained and the final amount of anesthetic solution

The Effect of Needle-free Injection System on Dental Injection Pain in Children: A Cross-over, Randomized Clinical Trial

were recorded. Precautions were taken to prevent tissue ballooning. After the treatment, duration of the analgesia effect (min) were also recorded. The presence of post-operative pain in patients was assessed via a phone call 1 day after the procedure.

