3.3.3 Subjective assessment

Pain levels were subjectively evaluated using the Wong-Baker Faces Pain Rating Scale (WB PRS) (Wong DL, 1988), which measures the unpleasantness or affective dimension of a child's pain experience. The PRS consists of a set of cartoon faces with varying facial expressions ranging from a smile/laughter to tears, and each child is asked to select the facial expression that best represents his/her experience of discomfort. Each face has a numerical value ranging from 0 (smiling face, 'no hurt') to 5 (crying/screaming face, 'hurts worst'). This scale was explained to the children carefully in advance. Immediately after the each injection, the children were asked to rate the level of pain perceived during the administration, using the PRS.

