3.4 Data collection

A structured form was designed to collect information regarding

- (1) patient's age;
- (2) gender;
- (3) type of teeth injected
- (4) type of dental treatment (filling or pulpotomy);
- (5) total amount of local anesthetics (LAs) used (ml)
- (6) duration of the analgesia effect (min)
- (7) post-op pain (after one day)
- (8) score on WB PRS after injection
- (9) score on FLACC during injection.

The Effect of Needle-free Injection System on Dental Injection Pain in Children: A Cross-over, Randomized Clinical Trial

Statistical Analysis

Post hoc power analysis was conducted for the study and the results of the comparison between the injection systems and Wong Baker scores were evaluated. According to this, with a total data set of 28 individuals, consisting of two independent groups and two dependent measurements, the power of the study was found to be 0.94 according to the G*Power 3.9.1.4 program, based on the partial eta squared (η^2) value of 0.108 obtained with a 0.05 error margin from the repeated measures ANOVA. The data were statistically analyzed using SPSS software (version 15.0, SPSS). Paired t-tests or Wilcoxon nonparametric tests were used to compare data within groups over two time periods, according to check the distribution whether normally distributed or not. The Chi-square test (X^2 -test) was also used to compare discrete random variables. Spearman's Rho correlation coefficient was used to find any relationship between two continuous variables. A p-value ≤ 0.05 was considered statistically significant.

4. Results

Total of 28 children, consisting of 18 girls (64.3%) and 10 boys (35.7%) aged 6–12 years were involved in this study. Mean age was 8.07 years with a standard deviation of 1.41 years. At the end of this study, a total of 56 injections were obtained for 28 children as NF injection (n = 28) and TM injection (n = 28).

In the study, when the distributions of the parameters (gender, type of dental treatment, type of teeth, and post-operative pain) were evaluated according to the type of injection technique, it was found that there was no statistically significant difference between the groups. (Table 1)

Table 1. Distribution of injection techniques based on evaluation parameters

Variables		Needle Free (NF) n	Traditional Method (TM) n	Total	p
Gender	Girl	18	18	36	1,000
	Boy	10	10	20	
Type of dental treatment	Filling	22	14	36	0,051
	Pulpotomy	6	14	20	
Type of teeth injected	1 st primary molar	12	7	19	0,259

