	2 nd primary molar	16	21	37	
Post-op pain (after one day)	Pain	5	7	12	0,746
	No pain	23	21	44	

*The Chi-square test (X^2 -test) was also used to compare discrete random variables.

Accordingly Table 2, in the group that received Needle-Free anesthesia in the first session and Traditional Method in the second session, the Wong-Baker scores were 4.44 ± 3.28 and 1.55 ± 0.88 , respectively. On the other hand, in the group that received Traditional Method anesthesia in the first session, the WB score was 1.68 ± 1.91 , while in the Needle-Free anesthesia group, the WB score was 2.52 ± 2.56 . In both cases, regardless of the method of anesthesia applied first, no statistically significant difference was found in the two groups. In the FLACC scores, for the Traditional Method - Needle Free group significant change was observed ($p = 0.025$) while for the Needle Free- Traditional Method group no statistically significant difference was observed ($p=0.141$). There were significant differences in the Amount of Anesthetic Solution (ml) and Duration of the Analgesia Effect (min) between the first and second visits for both injection methods, respectively as $p=0.003$ for NF-TM and $p<0.0001$ for

The Effect of Needle-free Injection System on Dental Injection Pain in Children: A Cross-over, Randomized Clinical Trial

TM-NF groups. The amount of anesthetic solution used for the 1st visit NF injection was $0,91\pm 0,48$ ml and $0,65\pm 0,30$ ml was for the 2nd visit NF injection. These amounts were statistically lower than TM injection in both visits. In the first visit, the mean duration of the analgesia effect in the NF group was 85.00 ± 39.05 min, whereas in the second visit, the mean duration for NF injection was found to be 90.26 ± 43.25 min. In the TM group, the mean anesthesia duration for the first and second visits was 140.00 ± 59.97 min and 130.00 ± 50.74 min, respectively. Regardless of the visit in which it was first applied, the duration of the analgesia effect in the NF group was found to be statistically significantly shorter than in the TM group ($p < 0,001$).

Table 2: Comparison of the 1st visit and 2nd visit measurements for continuous random variables in Needle Free-Traditional Method and Traditional Method - Needle Free

	1 st visit	2 nd visit	p
Wong Baker (WB) Scores			
Needle Free-Traditional Method	4,44±3,28	1,55±0,88	0,056
Traditional Method - Needle Free	1,68±1,91	2,52±2,56	0,119
FLAAC			

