in different sequences over two sessions. The analysis showed no statistically significant differences between the groups (Table 3). Similarly, present study evaluated the impact of the type and sequence of restorations (filling-filling, filling-pulpotomy, pulpotomy -filling) on Wong-Baker and FLACC scores for needle-free and traditional method injections administered in different sequences over two sessions. Results demonstrated that there were no statistically significant differences between the groups (Table 4).

Table 4: Wong-Baker and FLACC Scores in Needle Free-Traditional Method and Traditional Method - Needle Free groups based on type of dental treatment

	Type of Dental Treatment	Needle Free-Traditional Method Group		p	Type of Dental Treatment	Traditional Method-Needle Free Group		p
		1 st visit Needle Free	2 nd visit Traditional Method			1 st visit Traditional Method	2 nd visit Needle Free	
Wong Baker	Filling-Filling N=4	7, (3-9.5)	2, (0.5-2)	0,109	Filling-Filling N=8	2, (0.5-2)	2, (0.5-5.5)	0,167
	Filling-Pulpotomy N=3	4, (2-4)	2, (0-2)	0,180	Filling-Pulpotomy N=2	0, (0-0)	1, (0-1)	0,317
	Pulpotomy-Filling N=2	1, (0-1)	2, (2-2)	0,317	Pulpotomy-Filling N=9	2, (0-3)	2, (0-4)	0,655
FLACC	Filling-Filling N=4	0.5, (0-2.5)	0, (0-0)	0,180	Filling-Filling N=8	0, (0-0)	1, (0-1)	0,096
	Filling-Pulpotomy N=3	1, (0-1)	0, (0-0)	0,180	Filling-Pulpotomy N=2	0, (0-0)	0.5, (0-0.5)	0,317
	Pulpotomy-Filling N=2	0, (0-0)	0.5, (0-0.5)	0,317	Pulpotomy-Filling N=9	0, (0-1)	1, (0-1)	0,257

*Wilcoxon nonparametric test was used

*Needle Free-Traditional Method group: 1st visit Needle Free and 2nd visit Traditional Method was used for injection.

*Traditional Method - Needle Free group: 1st visit Traditional Method and 2nd visit Needle Free was used for injection

*The values are presented as Median, (Inter Quartile Range)

*filling-filling group: 1st visit filling and 2nd visit filling restoration have been done

*filling-pulpotomy group: 1st visit filling and 2nd visit pulpotomy restoration have been done

*pulpotomy-filling group: 1st visit pulpotomy and 2nd visit filling restoration have been done

Table 5. Amount of Anesthetic Solution (ml) in Needle Free-Traditional Method and Traditional Method - Needle Free groups based on type of dental treatment

	Type of Dental Treatment	Needle Free-Traditional Method Group		p	Type of Dental Treatment	Traditional Method-Needle Free Group		p

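### Tooth type is collected and known before the injection, and it differs between the two injections in 5 to 19 of 28 children, but no pain comparison uses it; Table 4 instead credits injection pain to a restoration done after scoring.

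*Combined protocol and SAP*

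**What the plan says.** Section 3.3 sets a paired design: "children received both types of injections before filling/pulpotomy treatment on their maxillary primary molars in two separate appointments". Section 3.2 requires bilateral maxillary primary molars of similar operative difficulty, but not the same tooth on both sides. Section 3.4 lists "3) type of teeth injected" on the data form. Section 4 confirms the pairing: "a total of 56 injections were obtained for 28 children as NF injection (n = 28) and TM injection (n = 28".

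Tooth type then appears once, in Table 1: "1 st primary molar 12 7 19 0,259" and "2 nd primary molar 16 21 37" (columns NF, TM, total; p on the first row).

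Pain is compared by sequence (Table 2), by gender (Table 3) and by restoration (Table 4). It is also correlated with age, volume and duration. None of these analyses uses tooth type. The text before Table 4 says the "present study evaluated the impact of the type and sequence of restorations" on Wong-Baker and FLACC.

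On timing, section 3.3.3 says: "Immediately after the each injection, the children were asked to rate the level of pain perceived during the administration". The data form in 3.4 places FLACC during the injection. Sections 3.3.1 and 3.3.2 both state: "After 5 min the treatment commenced".

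**The concern.** A within-child comparison removes whatever the two injections share. It does not remove a feature of the site that differs between them. Which molar is infiltrated is such a feature: it is fixed before the needle or device touches the mucosa, and it is already on the form. If first and second molar sites hurt differently, an unequal split by technique enters the NF minus TM difference and nothing in the analysis takes it out.

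Table 4 does not fill this gap. It splits the pain scores by a procedure that starts after the score at that visit has been recorded. The visit-2 restoration follows both scores, so the filling-filling and filling-pulpotomy rows, as procedures performed, differ only in something that happened after all the pain data were in.

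**Working it through.** **Reproducing the Table 1 p-value.** Table: 12 and 16 under NF, 7 and 21 under TM. Chi-square with continuity correction:

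56 × (|12×21 − 7×16| − 28)² / (19 × 37 × 28 × 28) = 56 × 112² / 551,152 = 1.27, p = 0.259.

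This matches the printed value. The test treats the 56 injections as independent, although they are 28 pairs.

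**How many pairs differ.** Let *a* be the number of children with a first molar injected at both visits (0 to 7). The margins fix the rest:

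- NF first, TM second: 12 − *a*
- NF second, TM first: 7 − *a*
- second molar at both: 28 − *a* − (12 − *a*) − (7 − *a*) = 9 + *a*
- pairs that differ: (12 − *a*) + (7 − *a*) = 19 − 2*a*
- same-tooth pairs: 28 − (19 − 2*a*) = 9 + 2*a*

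| *a* | Differing pairs | Split | Same-tooth pairs | Exact McNemar p |
|---|---|---|---|---|
| 0 | 19 (68%) | 12 v 7 | 9 | 0.359 |
| 7 | 5 (18%) | 5 v 0 | 23 | 0.0625 |

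The net excess under NF is 5 whatever *a* is. The paired table is not reported, so the position within these bounds is unknown.

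**Effect on the pain difference.** Let δ be the mean difference in score between first and second molar sites. This is an assumption; the documents give no value. Over all 28 children the NF minus TM mean shifts by (12 − 7)/28 × δ = 0.18δ.

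For scale only, weighting the two sequences of Table 2 by their sizes (9 and 19, from Table 3) gives a Wong-Baker difference of [9 × (4.44 − 1.55) + 19 × (2.52 − 1.68)]/28 = 41.97/28 = 1.5. With δ of 1 to 2 points the shift is 0.18 to 0.36, or 12% to 24% of that figure. The report does not give this pooled 1.5. It analyses each sequence separately, and the tooth counts by sequence are not shown, so the shift in either reported comparison cannot be computed.

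**Table 4 counts against Table 1.** Adding up the group sizes in Table 4:

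| | Filling | Pulpotomy | Table 1 |
|---|---|---|---|
| NF | 4+3+8+9 = 24 | 2+2 = 4 | 22 / 6 |
| TM | 4+2+8+2 = 16 | 3+9 = 12 | 14 / 14 |

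The two tables disagree by two procedures in each arm.

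**The case against.** The strongest reply is that allocation was by coin, so a 12 v 7 split needs no explanation beyond chance. No possible pairing gives an exact p below 0.05, and a chance imbalance does not invalidate an unadjusted paired comparison. That stands. A reader might infer a systematic excess of first molars under NF, or a biased comparison; the documents support neither.

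Nor do they show that tooth type affects injection pain. Even the assumed shift is modest. Standard errors backed out of the Table 2 p-values (0.056 with 9 children, 0.119 with 19) are about 1.29 and 0.51. The pooled standard error is then √[(9/28 × 1.29)² + (19/28 × 0.51)²] = 0.54, and 0.18 to 0.36 is 0.3 to 0.7 of it. This limits the point to a covariate worth including.

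On Table 4, the need for a filling or pulpotomy may mark the tooth's condition before the injection, and the children were enrolled because they already needed treatment. The documents do not say when the choice was made. The visit-1 restoration also precedes the visit-2 score. So it would be too strong to call the split meaningless; what fails is the causal wording for the same-visit or a later restoration. A score taken after a top-up injection during treatment could follow the start of the restoration, but the form lists only one Wong-Baker and one FLACC score.

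Pain is also split by gender, so restoration is not the only stratifier.

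**Conclusion.** The point holds as an omitted covariate and a wording problem. The count of 5 to 19 children rests only on the Table 1 margins and on one NF and one TM injection per child. The 0.18δ shift also needs a site difference δ, whose size and sign are unknown, and it applies to an overall difference that the report does not present. The Table 1 p-value does not settle the matter: it ignores the pairing, and a non-significant balance test does not show that the sites are equivalent.

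A reader might conclude that adjustment would overturn a reported result. Nothing in the documents shows that.

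The description of Table 4 is not supported for the same-visit or later restoration, given the stated order of scoring and treatment, and its strata are uncertain until the counts agree with Table 1.

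**What to change.** 1. Analyse Wong-Baker and FLACC in a within-child NF v TM model with technique, visit and tooth type. Equivalently, regress each child's NF minus TM difference on the tooth difference (−1, 0, +1), with sequence included to carry the visit effect. Show the result beside the unadjusted one.
2. Replace the tooth row of Table 1 with the NF-tooth by TM-tooth cross-table, overall and by sequence.
3. Treat an analysis of same-tooth pairs as a sensitivity check only. It would hold 9 to 23 children and may say little.
4. Reword the text on Table 4 so that the same-visit or later restoration is not said to act on injection pain. If the split is kept, label it as the tooth's treatment need, and first reconcile its counts with Table 1.

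The cost is one degree of freedom, one table row and a few lines of text. No new data are needed.

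### The post hoc power of 0.94 is not supported by the partial eta squared of 0.108 it is based on, and 0.108 does not appear to be the injection-technique effect

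*Combined protocol and SAP*

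**What the plan says.** The Statistical Analysis section (following the list in 3.4 Data collection) says that, for the post hoc power analysis, "the results of the comparison between the injection systems and Wong Baker scores were evaluated". The design inputs are 28 individuals, "consisting of two independent groups and two dependent measurements". The result is that "the power of the study was found to be 0.94 according to the G*Power 3.9.1.4 program, based on the partial eta squared", and the effect size is given as "0.108 obtained with a 0.05 error margin from the repeated measures ANOVA".

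The section gives no F, no p-value, no name for the ANOVA term, no correlation between the two measurements and no effect-size convention. The ANOVA itself does not appear in section 4, Results. What appears there for Wong-Baker is a paired t-test within each sequence (Table 2): p = 0.056 for needle-free first and p = 0.119 for traditional first. The text summarises both by saying that "no statistically significant difference was found in the two groups".

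**The concern.** A partial eta squared and its degrees of freedom fix the F statistic, the p-value and the observed power. An effect that lands exactly on p = 0.05 with 1 and 26 df has observed power of only 0.51. An effect of 0.108 falls short of significance, so it cannot carry a power of 0.94.

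The section also says the power concerns the comparison of injection systems. In an ANOVA with two sequence groups and two visits, that comparison is the group-by-visit term. The visit main effect is the period effect, and the two are easily confused when reading software output.

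What is at stake is interpretation. A reader who sees 0.94 beside two non-significant Wong-Baker tests would take them as good evidence that the techniques do not differ in reported pain. Those tests split the trial into 9 and 19 children, and no combined crossover estimate is given.

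**Working it through.** **Inputs.** Partial eta squared 0.108, N = 28, two groups, two measurements and alpha 0.05 come from Statistical Analysis. Wong-Baker means and paired t-test p-values come from Table 2. Sequence sizes come from Table 3: 6 + 3 = 9 (needle-free first, NF-TM) and 12 + 7 = 19 (traditional first, TM-NF). Error df = 28 − 2 = 26.

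**1. Reproducing 0.94.** f² = 0.108/0.892 = 0.1211, so f = 0.348. Assume the noncentrality is λ = f² × N × m/(1 − ρ), with m = 2. At ρ = 0.5, λ = 0.1211 × 28 × 2/0.5 = 13.56, and the noncentral F on 1 and 26 df gives power 0.943. On this route:

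| ρ | Power |
|---|---|
| 0 | 0.71 |
| 0.3 | 0.85 |
| 0.5 | 0.943 |
| 0.6 | 0.977 |

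Only ρ from about 0.48 to 0.504 rounds to 0.94. Entering f = √0.108 instead gives 0.917 at ρ = 0.5 and rounds to 0.94 at ρ of 0.54 to 0.55. Either way an unstated convention and a correlation of about 0.5 are needed.

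**2. What 0.108 implies.** F = 0.1211 × 26 = 3.15, p = 0.088. Observed power is 0.401 with λ = f² × 26 = 3.15, or 0.426 with λ = f² × 28 = 3.39. A partial eta squared from ANOVA output already reflects the within-child correlation, so dividing by (1 − ρ) counts that correlation twice. This points to the effect-size convention and not to a slip of arithmetic.

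**3. Which effect 0.108 is.** Differences are visit 2 minus visit 1.

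- NF-TM: d₁ = 1.55 − 4.44 = −2.89. With p = 0.056 on 8 df, t = 2.23, so SD = 2.89 × √9/2.23 = 3.88 (t unrounded).
- TM-NF: d₂ = 2.52 − 1.68 = +0.84. With p = 0.119 on 18 df, t = 1.64, so SD = 0.84 × √19/1.64 = 2.24 (t unrounded).
- Pooled SD = √[(8 × 3.88² + 18 × 2.24²)/26] = 2.85. Standard error of half a contrast = ½ × 2.85 × √(1/9 + 1/19) = 0.576.

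| Term | Estimate | F | Partial eta squared |
|---|---|---|---|
| Visit, (d₁ + d₂)/2 | −1.025 | 3.17 | 0.109 |
| Technique, (d₂ − d₁)/2 | +1.865 | 10.49 | 0.287 |
| Technique, weighted by sequence size | +1.50 | 7.77 | 0.230 |
| Technique, paired, sequence ignored (1, 27 df) | +1.50 | 7.19 | 0.210 |
| Technique, unpaired (1, 54 df) | – | 5.69 | 0.095 |
| Sequence | – | 1.49 | 0.054 |

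Allowing for rounding in Table 2, the visit value lies in 0.106 to 0.112 and the first three technique values in 0.285–0.290, 0.229–0.231 and 0.209–0.211. The unpaired analysis comes near 0.108 but is not a repeated measures ANOVA. The reported value matches visit.

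**4. What the combined contrast looks like.** The variance ratio of the differences is (3.88/2.24)² = 3.0, with the larger variance in the smaller group. Without assuming equal variances, the standard error is ½ × √(3.88²/9 + 2.24²/19) = 0.696. Then t = 1.865/0.696 = 2.68 on 10.6 df, p = 0.022, 95% CI 0.33 to 3.40. With pooled variance the p-value is 0.003 and the interval 0.68 to 3.05. Observed power for technique would be about 0.68 (unequal variances) or 0.88 (pooled). These two powers show only how far such a figure depends on assumptions; they are not replacements.

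**5. Scale check.** Section 3.3.3 says "Each face has a numerical value ranging from 0" up to 5. Table 4 prints a Wong-Baker quartile of 9.5. In Table 2 a mean of 4.44 with n = 9 allows an SD of at most √(4.44 × 0.56 × 9/8) = 1.67 on a 0 to 5 scale; the printed SD is 3.28.

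**The case against.** The strongest reply is that 0.94 against 0.40 is the wrong contrast. If 0.108 is the visit effect, then 0.40 is not the power for technique. In the pooled ANOVA the technique effect has observed power of about 0.88, so the printed figure would be too high by about 0.06, not by half. That is right as far as it goes, and 0.40 should not be quoted as the power for technique. It does not rescue the sentence, which bases 0.94 on 0.108. The 0.88 also relies on equal variances in the two sequences; without that assumption it is about 0.68.

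A second reply is that the harm is predicted and not documented: no results text refers to power or claims equivalence, and the figure enters no test or estimate. This stands, and it limits the seriousness of the point.

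Third, preferring unequal variances is partly a judgement, because a ratio of 3.0 on 8 and 18 df is borderline (p about 0.05). Both intervals are therefore shown, and both exclude zero.

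Finally, the route to 0.94 is conjecture, since neither the convention nor the correlation is given. That is accepted. The mismatch between 0.108 and 0.94 does not depend on it.

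**Conclusion.** The concern holds. From the section's own inputs, 0.108 on 1 and 26 df gives p = 0.088 and observed power of 0.40 to 0.43, not 0.94. This part needs only the stated figures.

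Two further conclusions are inferences. That 0.94 arose from a convention multiplying f² by N × m/(1 − ρ) with ρ about 0.5 is an assumption that reproduces the figure. That 0.108 is the visit effect rests on rounded means and p-values, sequence sizes taken from Table 3 and a standard two-sequence, two-visit ANOVA; the original output should settle it.

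Correcting the calculation would not make it useful, because observed power adds nothing to the p-value it comes from. The informative quantity is the crossover difference with its interval. It is not reported, and on the Table 2 summaries it points to higher Wong-Baker scores with needle-free injection. That estimate is only an indication: it assumes no carryover, and the companion tables contain errors. For example, Table 3 prints a median of 4.1 outside its own interquartile range of 2 to 4. The point should be fixed, but it does not undermine any test already reported.

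**What to change.** - Delete the sentence reporting 0.94 and do not substitute another post hoc power.
- State whether a prospective sample size calculation was made, and cite it if so. None appears in the available text, which starts at section 3.1.
- Beside the within-sequence tests, report the needle-free minus traditional Wong-Baker difference from a crossover analysis of the individual data, with a 95% CI, by a method that does not assume equal variances in the two sequences. State the no-carryover assumption. The +1.87 (0.33 to 3.40) above is not text to insert.
- Check the ANOVA output to establish which term gave 0.108.
- Before interpreting the difference in points, reconcile the Wong-Baker range in section 3.3.3 with the values in Tables 2 and 4.

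The cost is one deleted sentence and one reanalysis of existing data. A favourable figure is lost, and the Wong-Baker result can no longer be summarised only as non-significant within each sequence.

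### The repeated measures ANOVA behind the power figure pools Wong-Baker variances that Table 2 suggests are unequal across sequences; a 28-child technique estimate should use separate variances, and the 0.94 should be withdrawn

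*Combined protocol and SAP*

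**What the plan says.** The Statistical Analysis section describes a post hoc power analysis of the Wong-Baker comparison, "with a total data set of 28 individuals, consisting of two independent groups and two dependent measurements". It rests on a partial eta squared "value of 0.108", "obtained with a 0.05 error margin from the repeated measures ANOVA", and concludes that "the power of the study was found to be 0.94". This is the only mention of the ANOVA. No F statistic, p-value, confidence interval or variance check from it appears.

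The comparisons actually reported are paired tests run separately in each sequence. For children who had the needle-free injection first, "the Wong-Baker scores were 4.44 ± 3.28 and 1.55 ± 0.88" (Table 2, p=0.056). For those who had the traditional injection first, "the WB score was 1.68 ± 1.91 , while in the Needle-Free anesthesia group, the WB score was 2.52 ± 2.56" (p=0.119). The Table 2 footnote names the paired t-test. Table 3 gives the sequence sizes: 6+3=9 and 12+7=19. The Results text reads the two p-values as no significant Wong-Baker difference whichever technique came first.

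**The concern.** A two-sequence, two-visit repeated measures ANOVA tests technique (the sequence-by-visit term) and visit with one error variance, which it assumes is the same in both sequences. When the smaller group has the larger variance, pooling gives too much weight to the quieter, larger group and understates the standard error. The sequences here are 9 and 19, and the spread in Table 2 points that way.

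What is at stake is chiefly the next step. The reported tests split a 28-child crossover into two small pieces, and neither estimates the technique effect from everyone. The obvious repair is a combined estimate, and the model already named in the analysis section is the obvious one to use. As it stands, that model would give an interval that is too narrow.

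**Working it through.** **1. The stated power.** f² = 0.108/0.892 = 0.121. With λ = f² × N × m/(1−ρ), N = 28, m = 2 and ρ = 0.5 (my assumption; the document gives no correlation), λ = 13.56. The F test on 1 and 26 df then has power 0.943, which reproduces 0.94. The observed eta squared already reflects the pairing, so the factor for ρ counts it again. With λ = f² × 26 = 3.15, power is about 0.40.

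**2. Variance of the visit difference** (visit 1 minus visit 2). SD = |mean difference| × √n / t, with t taken from the printed two-sided p.

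| Sequence | n | Mean difference | p | t (df) | SD | Variance |
|---|---|---|---|---|---|---|
| Needle-free first | 9 | 4.44 − 1.55 = 2.89 | 0.056 | 2.233 (8) | 3.88 | 15.1 |
| Traditional first | 19 | 1.68 − 2.52 = −0.84 | 0.119 | 1.637 (18) | 2.24 | 5.0 |

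The variance ratio is 3.01 and the SD ratio 1.74. Rounding in Table 2 allows 2.90 to 3.13. As a check on the paired-t reading, nine pairs compatible with the Table 4 medians and quartiles have differences 0, 4, 6, 10, 0, 2, 6, −2, 0. These give variance (196 − 26²/9)/8 = 15.1 and paired p = 0.056.

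**3. Was the variance pooled?** Pooled variance = (8 × 15.07 + 18 × 5.00)/26 = 8.10. Standard error of a contrast between sequences = √(8.10 × (1/9 + 1/19)) = 1.152. Partial eta squared = F/(F + 26).

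- Visit: contrast 2.89 − 0.84 = 2.05, F = 3.17, eta squared 0.1086. With the means as the group sizes imply them (40/9, 14/9, 32/19, 48/19), F = 3.15 and eta squared is 0.108, the printed value.
- Technique: contrast 2.89 + 0.84 = 3.73, F = 10.49, eta squared 0.287.

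So the pooled model fits the printed 0.108, and it does so for the visit term.

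**4. Separate variances.** Standard error = √(15.07/9 + 5.00/19) = √(1.674 + 0.263) = 1.392, which is 1.21 times the pooled value. Satterthwaite df = 10.6 against 26. The technique effect is half the contrast: 3.73/2 = 1.87.

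| | Pooled | Separate |
|---|---|---|
| Half-width | 2.056 × 1.152/2 = 1.18 | 2.211 × 1.392/2 = 1.54 |
| 95% CI | 0.68 to 3.05 | 0.33 to 3.40 |
| Technique p | 0.003 | 0.022 |
| Visit p | 0.087 | 0.17 |

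The half-width ratio is 1.54/1.18 = 1.30.

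**5. Error of a nominal 5% pooled test** (n = 9 and 19, normal differences, numerical integration; 1,000,000 simulations at the observed ratio agree).

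| True variance ratio | Pooled error |
|---|---|
| 1 | 5.0% |
| 1.5 | 6.8% |
| 2 | 8.2% |
| 3.0 | 10.4% |

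At ratio 3 the separate-variance test has about 5.1%. The 95% interval for the ratio is 1.00 to 12.2 (F on 8 and 18 df, p = 0.0495), which gives an error of 5.0% to 16.6%.

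**6. The sequence effect.** It uses each child's sum, with variance 2(s₁² + s₂²) minus the difference variance: 2(3.28² + 0.88²) − 15.07 = 8.0 and 2(1.91² + 2.56²) − 5.00 = 15.4. Here the larger variance lies in the larger group, and the pooled test is conservative, at about 3%.

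**The case against.** The strongest reply is that nothing printed depends on the pooled error term except the 0.108 and the 0.94. That is right. A reader might infer that the trial's reported p-values are too small or its intervals too narrow. The documents do not support this: no ANOVA p-value or interval is given, and the Table 2 paired tests use each sequence's own variance.

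Four other strong readings also fail.

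- Not every ANOVA effect is liberal; the sequence effect goes the other way (step 6).
- The fault cannot be charged to a FLACC ANOVA, because the section ties the model to Wong-Baker scores only. The FLACC variance ratio is about 2.1, with F-test p = 0.17.
- The ANOVA is not the only analysis of pain in all 28 children. Table 1 compares post-operative pain on all 56 procedures, and the Spearman correlations are not described as split by sequence.
- The 10% is not an established error rate. It takes a ratio estimated with nine children in one group as the truth and assumes normality for scores on a few faces. The ratio also depends on implied visit correlations of −0.61 in one sequence and +0.53 in the other. With +0.53 in both, it would be 1.7 and the error about 7.4%.

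Finally, no conclusion at 0.05 changes: technique is significant and visit is not, under either method. All of this limits the weight of the point. It does not make pooling a good choice, since separate variances keep close to 5% error when the variances are equal.

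**Conclusion.** The point holds as a limited one. The ANOVA pools variances that the document's own figures suggest are unequal, in the unfavourable direction for technique and visit. The likely error of a nominal 5% test is about 10% at the observed ratio, but values from 5.0% to 16.6% are compatible with the data. This rests on the Table 2 p-values being paired t-tests, as the footnote says, and on roughly normal differences. The 1.87 also assumes that any carry-over is the same in both sequences.

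The practical gain lies in reporting a combined technique estimate at all. Two split tests, each read as no difference, give way to a 28-child estimate whose interval excludes zero, with a lower limit of 0.33 where the pooled version would give 0.68. Separately, the 0.94 does not describe power for the injection comparison: the effect size behind it matches the visit term (0.108), while the technique term is 0.287 in the same pooled model.

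**What to change.** In the Statistical Analysis section, state that the technique effect is estimated from all 28 children by comparing within-child visit differences between the two sequences with separate variances (Welch/Satterthwaite, or a studentised permutation test given the coarse scores). Report half the contrast with its 95% interval. From the summary data this is 1.87 (0.33 to 3.40), p=0.022, to be confirmed on the individual records.

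Withdraw the 0.94. Do not recompute post hoc power from the new standard error; the interval conveys the precision.

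The cost is one sentence in the analysis section, removal of the power statement, and a re-run on existing data. The downside is an interval about 30% wider than the pooled one and a less favourable p-value.
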